### 5.6.1. Extent of Exposure

The number and percentage of participants who receive each study agent within a study intervention will be summarized.

Descriptive statistics for duration of each study agent within a study intervention (N, mean, SD, median, and range (minimum, maximum)) during the treatment period will be summarized. The duration of treatment with NA will be also summarized for the follow-up phase by intervention arm.

Because of the different route and frequency of treatment administration across the 3 agents (for JNJ-3989 one subcutaneous injection once every 4 weeks, for PegIFN- $\alpha$ 2a one subcutaneous injection weekly and for NA once daily tablet) the total duration for each study treatment as follows:

- JNJ-3989:  $[\text{Min} ((\text{Date of last JNJ-3989 injection in the given phase} + 27 \text{ days}), \text{Date of discontinuation from JNJ-3989}, \text{Date of trial disposition}, \text{cut-off date}) - \text{Date of first JNJ-3989 injection in the given phase} + 1] / 7$
- PegIFN- $\alpha$ 2a:  $[\text{Min} (\text{Date of the last PegIFN-}\alpha\text{2a injection} + 6 \text{ days}, \text{Date of discontinuation from PegIFN-}\alpha\text{2a}, \text{Date of trial disposition}, \text{cut-off date}) - \text{Date of first PegIFN-}\alpha\text{2a injection} + 1] / 7$
- NA:  $[\text{Min} (\text{Date of the last NA administration in the given phase}, \text{Date of discontinuation from NA}, \text{Date of trial disposition}, \text{Date of clinical cut-off}) - \text{Date of first NA administration date in the given phase} + 1] / 7$

For NA treatment, the total duration of exposure will be calculated separately for treatment period and FU phases. For FU, the total duration will add up the weeks of NA treatment post-treatment period for those participants during the NA re-treatment weeks. Those participants who never restarted NA treatment after Week 24 will be counted as having zero weeks of NA exposure during the FU.

Cutoff dates will be defined to match the prespecified timepoints for interim analyses and the primary analysis, respectively (Section 5.8).

The number and percentage of participants who skipped any dose of JNJ-3989 or PegIFN- $\alpha$ 2a or NA will be summarized separately for each study intervention by intervention arm during the

treatment period. Additionally, the number and percentage of participants who missed 2 or more JNJ-3989 injections, or who missed more than 5 doses of NA within a four-week period or who missed 2 or more PegIFN- $\alpha$ 2a injections will be presented.

Study intervention compliance will be summarized descriptively. See [Appendix 7](#) for further details.

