6.5.1. NA Treatment Completion

All participants will receive the last dose of JNJ-3989 at Week 24 and the last dose of PegIFN- α 2a at Week 23 (Arms 1 and 2) or Week 11 (Arm 3). They will start the FU Period after the Week 24 visit. If all of the following NA treatment completion criteria are met based on the Week 24 results, treatment with NA will be stopped at the next scheduled visit (ie, FU Week 2):

- The participant has ALT <3x ULN, AND
- The participant has HBV DNA <60 IU/mL at Week 24 and HBV DNA <LLOQ at the previous visit, or HBV DNA <LLOQ at Week 24, AND
- The participant is HBeAg-negative, AND
- The participant has HBsAg <100 IU/mL.

Note: Participants who are close to meeting the protocol-defined NA treatment completion criteria with the Week 24 results, and do meet the criteria based on the FU Week 2 results may be allowed to stop NA at FU Week 4, after consultation with the Sponsor. In case of ALT elevation \geq 3x ULN at Week 24, the investigator must consider different potential causes of increased ALT to ensure appropriate work up and management as needed. If the ALT elevation is unrelated to HBV activity and/or <3x ULN by FU Week 2, NA completion may be considered at the discretion of the investigator and in consultation with the sponsor.

Participants who do not meet the above criteria based on the Week 24 or FU Week 2 results should continue NA treatment during the 48-week FU Period.

Participants who meet the above-mentioned NA treatment completion criteria will be monitored closely during the 48-week FU Period with a study visit at least once every 4 weeks. NA treatment should be re-started in accordance with the NA re-treatment criteria (see Section [6.5.2](#), NA Re-treatment Criteria During Follow-up, for more details).

The investigator should consider to re-start NA treatment per local standard of care at the EOS visit (Follow-up Week 48) for participants who met the NA treatment completion criteria based on the Week 24 (or FU Week 2) results, who did not re-start NA treatment during the follow-up phase, and who did not achieve and maintain HBsAg seroclearance. NA will not be provided by the sponsor after the final study visit.

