Week 2), otherwise NA treatment will continue during the complete FU period. Note: Participants who are close to meeting the protocol-defined NA treatment completion criteria with the Week 24 results, and do meet the criteria at FU Week 2 results may be allowed to stop NA at FU Week 4, upon prior discussion with the Sponsor.

The NA treatment completion criteria which take ALT, HBV DNA, HBeAg, and HBsAg levels into consideration, have been selected to ensure that only participants with a higher chance of achieving sustained off-treatment response are allowed to stop all study intervention. Participants who meet the protocol-defined NA treatment completion criteria will be monitored closely during the 48-week FU Period and participants should re-start NA treatment if NA re-treatment criteria are met (see Clinical Protocol Section 6.5.2, NA Re-treatment Criteria During Follow-up, for more details).

If a participant prematurely discontinues JNJ-3989 (ie, before Week 24), the participant will have an early WD visit and will enter the 48-week follow-up period as per the Schedule of Activities, unless the participant withdraws consent.

If a participant prematurely discontinues PegIFN- $\alpha$ 2a (ie, before Week 23 [Arms 1 and 2] or before Week 11 [Arm 3]), treatment with JNJ-3989 and NA should be continued as planned.

If a participant withdraws prematurely from the study, the reason for withdrawal (if known) should be documented in the case report form (CRF) and in the source document. Participants who withdraw consent will be offered an optional safety follow-up visit to occur on the day of consent withdrawal.

An internal Data Review Committee (DRC) will be commissioned for monitoring safety of participants enrolled in this study. In addition, an Independent Flare Expert Panel (IFLEP) will be appointed.

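### SAP 5.6.1 is wrong and self-contradictory on NA exposure in follow-up: its follow-up sentences count only re-treatment weeks, although most routes through follow-up include NA without a restart

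*SAP*

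**What the plan says.** SAP 5.6.1 announces the summary: "The duration of treatment with NA will be also summarized for the follow-up phase by intervention arm". It then gives two instructions for deriving it.

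- **General formula.** NA duration in weeks is an end date minus a start date, plus one, divided by seven, calculated separately for the treatment period and follow-up. The start is "Date of first NA administration date in the given phase". The end is the earliest of four dates: "Date of the last NA administration in the given phase", NA discontinuation, trial disposition and the clinical cut-off.
- **Follow-up sentences.** Directly after the formula: "For FU, the total duration will add up the weeks of NA treatment post-treatment period for those participants during the NA re-treatment weeks". Then: "Those participants who never restarted NA treatment after Week 24 will be counted as having zero weeks of NA exposure during the FU".

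On the design, Protocol 6.5.1 says participants who do not meet the completion criteria "should continue NA treatment during the 48-week FU Period". The note to Figure 1 in SAP 1.2 agrees: "otherwise NA treatment will continue during the complete FU period". Participants who meet the criteria on Week 24 results stop at FU Week 2. Those who meet them on FU Week 2 results may stop at FU Week 4 after consultation with the sponsor. Footnote o of the Protocol Schedule of Activities recognises two groups who receive NA in follow-up: those who could not stop, and those who met the re-treatment criteria.

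**The concern.** The follow-up sentences fit a design in which NA ends for everyone at Week 24 and any later NA is re-treatment. The current protocol is different. A continuer never stops, so there is nothing to restart, and the zero-weeks sentence on its plain wording captures that person. Participants who meet the criteria also take NA for the first 2 or 4 weeks of follow-up, and that is dropped as well.

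The sentences may be left over from the pre-amendment design. SAP Table 13 still has deviations for stopping or not stopping NA at Week 24 (items 45 and 46), and item 13 still carries the HBsAg threshold of 100 IU/mL that criterion A13.1 has lowered to 5. That origin is an inference; the conflict with Protocol 6.5.1 does not depend on it.

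What is at stake is the follow-up NA exposure table. SAP Table 10 sends extent of exposure to the Data Review Committee (DRC) at every data review, interim, primary and final analysis. If the follow-up sentences are programmed, an arm with many continuers could show less NA exposure than an arm with many restarters, although its actual use was higher.

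**Working it through.** **Inputs.** For an on-schedule participant, SAP Table 3 ends the treatment period the day before the Week 24 intake and starts follow-up the next day, so FU Day 1 is the Week 24 intake date. SAP Table 4 gives target days 15 (FU Week 2), 29 (FU Week 4), 169 (FU Week 24) and 337 (FU Week 48). The Schedule of Activities allows ±4 days at follow-up visits.

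**The plan's own figure.** The zero-weeks sentence gives 0 for anyone who never restarted.

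**Interval formula from SAP 5.6.1:** weeks = (last day − first day + 1)/7.

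1. Continuer, FU Day 1 to Day 337: 337/7 = 48.1 weeks. With the visit window, 333/7 = 47.6 to 341/7 = 48.7.
2. Stops at FU Week 2 with no restart, last dose Day 14 or 15: 14/7 = 2.0 or 15/7 = 2.1 weeks.
3. Stops at FU Week 4 with no restart, last dose Day 28 or 29: 28/7 = 4.0 or 29/7 = 4.1 weeks.
4. Restarter (example): stops Day 15, restarts Day 169, on NA to Day 337.
   - Actual: 15/7 + (337 − 169 + 1)/7 = (15 + 169)/7 = 26.3 weeks.
   - Re-treatment weeks only: 169/7 = 24.1 weeks.
   - General formula, no NA discontinuation date recorded for the first stop: 337/7 = 48.1 weeks, which includes the gap off NA.
   - General formula, Day 15 recorded as the NA discontinuation date: the minimum picks Day 15, giving 15/7 = 2.1 weeks.

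| Participant | Actual (weeks) | Follow-up sentences | General formula |
|---|---|---|---|
| Continues to Day 337 | 48.1 | 0 | 48.1 |
| Stops FU Week 2, no restart | 2.0–2.1 | 0 | 2.0–2.1 |
| Stops FU Week 4, no restart | 4.0–4.1 | 0 | 4.0–4.1 |
| Stops Day 15, restarts Day 169 | 26.3 | 24.1 | 48.1 or 2.1 |

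**Arm-level illustration.** The documents give no continuation rate, so a share c is assumed, with nobody restarting and all others stopping at FU Week 2. The actual mean is c × 48.1 + (1 − c) × 2.1.

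- c = 20%: 9.6 + 1.7 = 11.3 weeks
- c = 50%: 24.05 + 1.05 = 25.1 weeks
- c = 80%: 38.5 + 0.4 = 38.9 weeks

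The follow-up sentences report a mean of 0 in all three cases.

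**The case against.** The best reply is that the general formula is also in the section, applies by phase, and counts a continuer correctly at about 48 weeks. A programmer who follows it would not report continuers as unexposed. It can also be argued that restarting presupposes a stop, so the zero-weeks sentence was meant only for participants who stopped, and its error is then 2 to 4 weeks.

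Part of this stands. A reader might infer that continuers will certainly be tabulated at zero; the documents do not go that far, because two instructions compete. But the follow-up sentences are the specific ones for this phase, nothing says the formula prevails, and nothing exempts continuers. Even on the narrow reading, the restriction to re-treatment weeks remains.

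Three other stronger readings are not supported:

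- **That the formula always overstates exposure in restarters.** Its end term includes the NA discontinuation date, so it can understate instead (2.1 against 26.3 weeks).
- **That a particular total of person-weeks is lost.** No continuation rate is given, so only a range under stated assumptions is possible.
- **That adverse event, flare or renal results are distorted through a wrong denominator.** Adverse events are counts and percentages of participants (SAP 5.6.2). The flare section (5.4.2.1.14) speaks of an incidence rate but names no person-time denominator and does not refer to 5.6.1. Renal summaries (5.6.3.2) do not use this figure.

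SAP 5.4.2.1.2 and 5.4.2.1.3 also tabulate by arm who missed the completion criteria and who restarted NA, so a careful reader of the report could see that follow-up NA was not confined to restarters.

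**Conclusion.** The point holds as an error and an internal contradiction in one derivation. The follow-up sentences give 0 weeks where the design implies about 48 for continuers and about 2 to 4 for participants who stop and do not restart. The general formula gives a different value for the same people. Neither instruction recovers 26.3 weeks for the restarter example.

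The individual figures assume on-schedule visits and daily NA intake up to each stop; the restart on Day 169 is illustrative. Participants who leave JNJ-3989 early have no fixed NA stopping visit (Protocol 6.5.1), so their actual follow-up exposure may differ, but the same two rules would be applied to them.

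The reach is limited to the descriptive by-arm follow-up exposure summary in the safety report and the DRC outputs. No efficacy result, alpha or power changes. It should be corrected because the table can be materially wrong and the correction is simple.

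**What to change.** In SAP 5.6.1, delete the zero-weeks sentence and the restriction to re-treatment weeks. For every participant, define follow-up NA exposure as the sum of the actual NA dosing intervals falling in the follow-up phase, each counted as end minus start plus one and truncated at trial disposition or data cut-off. State that this replaces the single first-to-last-date formula for NA in follow-up, so that a gap off NA is not counted and a first stop does not cut off later re-treatment.

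The source is the Study Drug Administration for NA CRF page, which SAP 5.4.1.1.2 and 5.4.2.1.3 already use to identify restarts. Showing the summary separately for participants who continued, stopped, and stopped then restarted would help the reader but is optional.

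The cost is a short SAP wording change and one derivation. It needs no new data or visits and no change to clinical rules.

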**Table 3: Analysis Phases Start and End Dates**

Analysis Phase	Start Date	End Date
Screening	The date of signing the informed consent	1 day before the first study agent intake
Treatment period	Date of first study agent intake	
If participant did not withdraw from the study and did not discontinue treatment early prior to the projected/actual Week 24 Visit date:
 
Min [Date of Week 24 study agent intake – 1 day, cut-off dateb]
 
Otherwise:
 
Max [Early study withdrawal visit date, study agent discontinuation date] + 5 daysa or cut-off dateb, whichever occurs first

Follow-up	
Participants who did not withdraw informed consent during treatment period: End of treatment period + 1 day
 
Otherwise: missing
	Max [study discontinuation date, study completion date] or cut-off date b , whichever occurs first

a Addition of 5 days is only applicable for Adverse Events and Concomitant Medications.

b Cut-off dates will be defined to match the prespecified timepoints for DRC safety monitoring, interim analyses, the primary and the final analyses, respectively.

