## 5.6. Safety Analyses

Summaries will be provided on the overall population and by intervention arm and analysis phase unless specified otherwise.

Safety and tolerability will be assessed by evaluating treatment emergent-adverse events (TEAEs), physical examinations, ophthalmic examinations, vital signs measurements, clinical laboratory tests (including hematology, blood biochemistry, blood coagulation, and urinalysis), and ECGs.

For all continuous safety variables, descriptive statistics by intervention group will include the N, mean, standard deviation, median, minimum, and maximum. Categorical variables will be summarized by intervention group using frequency counts and percentages.

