44	For PegIFN- $\alpha$ 2a, dose adjustment guidelines are recommended for participants who develop laboratory abnormalities during PegIFN- $\alpha$ 2a treatment, as recommended in the locally approved prescribing information for PegIFN- $\alpha$ 2a	Subject developed laboratory abnormalities but did not receive any PegIFN- $\alpha$ 2a dose adjustment  Recommended dose adjustments: -ANC <750 cells/mm  Reduce to 135 $\mu$ g -ANC <500 cells/mm  Discontinue treatment until ANC values return to more than 1,000 cells/mm  Reinstigate at 90 $\mu$ g and monitor ANC - Platelet <50,000 cells/mm  Reduce to 90 $\mu$ g - Platelet <25,000 cells/mm  Discontinue treatment	Received wrong treatment or incorrect dose	If classified as major protocol deviation (reviewed case by case), excluded from PP set	Yes
45	Subject stopped NA treatment at week 24, although some relevant changes in participant baseline status with regards to ALT, HBV DNA levels and/or HBeAg status were observed at Week 20 or any other event that in the opinion of the investigator could prevent stopping NA, were observed	Subject stopped NA treatment at week 24, although some relevant changes in participant baseline status with regards to ALT, HBV DNA levels and/or HBeAg status were observed at Week 20 or any other event that in the opinion of the investigator could prevent stopping NA, were observed	Received wrong treatment or incorrect dose	If classified as major protocol deviation (reviewed case by case), excluded	Yes

				from PP set	
46	Subject did not stop NA treatment at week 24, although no relevant changes in participant baseline status with regards to ALT, HBV DNA levels and/or HBeAg status or no other events that in the opinion of the investigator could prevent stopping NA treatment, were observed	Subject did not stop NA treatment at week 24, although no relevant changes in participant baseline status with regards to ALT, HBV DNA levels and/or HBeAg status or no other events that in the opinion of the investigator could prevent stopping NA treatment, were observed	Received wrong treatment or incorrect dose	If classified as major protocol deviation (reviewed case by case), excluded from PP set	Yes

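### SAP 5.6.1 records zero weeks of follow-up NA for participants who took NA throughout follow-up

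*SAP*

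**What the plan says.** SAP 5.6.1 (Extent of Exposure) plans to summarise NA duration in the follow-up phase by intervention arm, and gives two ways to compute it.

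- **General NA formula, applied per phase.** Take the earliest of four dates: last NA administration in the phase, discontinuation from NA, trial disposition and clinical cut-off. Subtract the "Date of first NA administration date in the given phase", add one day and divide by 7. The section says this is done separately for the treatment period and follow-up.
- **Two follow-up sentences.** The first says that "the total duration will add up the weeks of NA treatment post-treatment period for those participants during the NA re-treatment weeks". The second says: "Those participants who never restarted NA treatment after Week 24 will be counted as having zero weeks of NA exposure during the FU".

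Other provisions decide who is on NA in follow-up:

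- Protocol 6.5.1: participants who do not meet the completion criteria on the Week 24 or FU Week 2 results "should continue NA treatment during the 48-week FU Period". Protocol 4.1 says the same.
- Protocol 6.5.1: those who meet the criteria on the Week 24 results stop NA at FU Week 2. Those who qualify on the FU Week 2 results may stop at FU Week 4 after consultation with the sponsor.
- SAP Table 3: for a participant who completes treatment, the treatment period ends the day before the "Date of Week 24 study agent intake", and follow-up starts the next day. FU Day 1 is therefore the Week 24 dosing date.

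**The concern.** The zero rule depends on whether NA was restarted, but only someone who stopped can restart. A participant who never stopped falls into the never-restarted group and is recorded as unexposed, although that participant has the longest exposure possible. The rule also drops NA taken between the Week 24 visit and the FU Week 2 or 4 stop.

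The follow-up NA table could therefore show low exposure in an arm where most participants stayed on NA, and could order arms the wrong way round. A programmer who follows the formula instead of the sentences would produce a different table from the same data.

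The wording would suit a design in which everyone stops NA at Week 24. SAP Table 13 has a deviation row of that kind: "Subject did not stop NA treatment at week 24, although no relevant changes in participant baseline status". That is a plausible origin for the sentence, not proof of it.

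**Working it through.** **Inputs.** FU Day 1 is the Week 24 dosing date (SAP Table 3). Target days are FU Week 2 = 15, FU Week 4 = 29, FU Week 24 = 169 and FU Week 48 = 337 (SAP Table 4). Assumptions: treatment period completed, visits on target days, no missed doses, NA taken up to and including the stop visit.

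**Plan's own figure.** The zero sentence gives 0 weeks to anyone who never restarted. That result is then compared with the section's own formula, (last day − first day + 1)/7, and with time actually on NA.

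| Participant | Two FU sentences | Per-phase formula | Actually on NA |
|---|---|---|---|
| Continues NA to FU Week 48 | 0 | (337 − 1 + 1)/7 = 48.1 | 48.1 |
| Stops at FU Week 2, no restart | 0 | (15 − 1 + 1)/7 = 2.1 | 2.1 |
| Stops at FU Week 4, no restart | 0 | (29 − 1 + 1)/7 = 4.1 | 4.1 |
| Stops at FU Week 2, restarts at FU Week 24 | (337 − 169 + 1)/7 = 24.1 | 48.1 or 2.1 (see below) | (15 + 169)/7 = 26.3 |

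**Restarter under the formula.** The formula takes a minimum that includes the date of discontinuation from NA. If that field holds the first stop (Day 15), the formula gives 2.1 weeks. If it is empty or holds the final stop, the formula gives 337/7 = 48.1 weeks, which includes the gap off NA of 48.1 − 26.3 = 21.9 weeks (unrounded 153/7). Neither equals 26.3. The correct figure appears only if the first stop date is used and the re-treatment weeks are then added: 2.1 + 24.1 = 26.3 after rounding.

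**Effect on an arm mean (shares assumed for illustration).**

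No restarts, a share s stopping at FU Week 2. The zero rule gives a mean of 0 whatever s is. The actual mean is 2.14s + 48.14(1 − s):

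- s = 0.2: 38.9 weeks
- s = 0.5: 25.1 weeks
- s = 0.8: 11.3 weeks

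With restarts, 34 per arm, about 20% of stoppers restarting at FU Week 24:

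- 10 continue, 24 stop, 5 of them restart: rule 5 × 24.14/34 = 3.6; actual (10 × 48.14 + 24 × 2.14 + 5 × 24.14)/34 = 19.2
- 17 continue, 17 stop, 3 restart: rule 2.1; actual (17 × 48.14 + 17 × 2.14 + 3 × 24.14)/34 = 27.3
- 24 continue, 10 stop, 2 restart: rule 1.4; actual (24 × 48.14 + 10 × 2.14 + 2 × 24.14)/34 = 36.0

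In this illustration the reported mean falls as true exposure rises.

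**The case against.** The authors may have had only stoppers in mind when they wrote that those who never restarted have no exposure. The text does not say so, and zero is still wrong for stoppers, who take NA for about two to four weeks of follow-up.

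A better defence concerns restarters. If the discontinuation date is the first stop and the re-treatment sentence is read as an addition to the formula, the plan gives the right answer for them. That stands, so it cannot be said without condition that the formula counts the off-NA gap. It does not help the other groups, because the zero sentence still overrides the formula for them.

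It is also fair that this is one descriptive output. NA status is reported elsewhere: completion criteria met (SAP 5.4.2.1.2), actual restarts with a cross-tabulation against the criteria (5.4.2.1.3), and discontinuations with reasons (5.2).

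A reader might go further and infer that the follow-up safety tables are defective because adverse events and graded laboratory results are not split by NA stopped versus continued. The documents do not support that. SAP 5.6 states the layout: "Summaries will be provided on the overall population and by intervention arm and analysis phase unless specified otherwise". This agrees with Protocol 9.4.3 and is valid as a summary of each randomised regimen. Off-treatment flares are analysed separately in those who stopped NA (SAP 5.4.2.1.14), and serious adverse events are listed (5.6.2). A split by NA status would be post-randomisation, with small cells. Protocol 9.4.3 also defers to the Master Protocol, which was not available. Such columns are a reporting preference.

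**Conclusion.** The follow-up NA exposure rule in SAP 5.6.1 is wrong as written and conflicts with the formula beside it. A participant on NA for the whole of follow-up is recorded as 0 instead of about 48.1 weeks, below a restarter at 24.1. A stopper who never restarts is recorded as 0 instead of about 2.1 or 4.1. These individual figures rest on target-day visits and full adherence; the arm means also rest on assumed shares.

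The consequence is confined to a descriptive exposure summary. A reader might infer that the off-treatment efficacy results are affected as well. They are not: whether NA was restarted is taken from the drug-administration CRF page (SAP 5.4.1.1.2), not from this duration, and no efficacy test uses it.

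**What to change.** In SAP 5.6.1, replace the two follow-up sentences with a single rule: *FU NA exposure is the sum of weeks actually on NA during FU (weeks continued from FU Day 1 until NA stop or end of FU, plus any re-treatment weeks), excluding periods off NA.* Say that this rule takes the place of the first-to-last formula for follow-up, so that the choice of discontinuation date no longer matters. Take start and stop dates from the *Study Drug Administration for NA* CRF page, which the SAP already uses to identify restarts.

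The cost is a short text change and the matching derivation. No new data are needed, and no safety table or efficacy analysis has to be redesigned.
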